## 5.3 LIFESTYLE CONSIDERATIONS

N/A

#### 5.4 SCREEN FAILURES

Screen failures are defined as participants who do not meet the study inclusion/exclusion criteria as determined during the initial phone screening assessment or initial in-person screening evaluation. A minimal set of screen failure information will be retained to ensure transparent reporting of screen failure participants, to meet the Consolidated Standards of Reporting Trials (CONSORT) publishing requirements and to respond to queries from regulatory authorities. Minimal information includes demography, screen failure details, and eligibility criteria.

Individuals who do not meet the criteria for participation in this trial (screen failure) because of a time sensitive factor (e.g., diagnosed concussion within the past 6 months) may be rescreened. Rescreened participants will be assigned the same participant number as for the initial screening.

## 5.5 STRATEGIES FOR RECRUITMENT AND RETENTION

High school-aged soccer athletes will be recruited primarily through the athletics programs at local high schools, following local approval at each individual institution. Coaches, managers, athletic trainers, or other team/athletics personnel will be asked to post and/or distribute paper and/or electronic recruitment materials to those athletes who are members of the school's soccer teams. In addition, we will also recruit through other non-school-based local soccer clubs, camps, and programs in a similar manner, including recruitment through local soccer and/or fitness facilities. Lastly, we will advertise on the Michigan Institute of Clinical Health Research (MICHR) UM Health Research website (https://umhealthresearch.org), in UMHS clinics, and through public advertisements and outreach as necessary. UM Health Research is a secure registry database that matches people to clinical research studies, and is supported by the Michigan Institute for Clinical and Health Research.

Interested individuals (and/or their parents/guardians if minors) will complete an initial self-reported screening evaluation (either electronically with phone review or during a single phone session, per individual preference and availability) with a member of the study to assess study inclusion and exclusion criteria and to describe the details of the study. Those who pass the initial screening assessment and are interested in participating after hearing full study details will be scheduled for a final in-person eligibility assessment by the PI, or his designee, which will include a targeted screening physical examination.

Potential subjects passing both components of the screening assessment will then be invited to enroll in the study and those wishing to do so will complete the informed consent process (assent for minors with accompanying parent/guardian consent). All subjects will provide written informed consent using UM IRB-MED approved informed consent documents with a qualified member of the study team. Minor children under the age of 18 will provide written assent and a parent/guardian will provide written consent. During the in-person consent process the consenting study team member will review the entire informed consent document with the subject (and parent/guardian when applicable), including all potential risks associated with the study and will provide an opportunity to ask any questions they may have.

To promote study recruitment and retention, subjects will be compensated for their participation in this study. Compensation will be incrementally disbursed upon successful completion of each of the four laboratory testing sessions, with greater amounts provided for each successive testing session to incentivize full study completion. Subjects will also receive a 4-month membership at a local fitness facility as well as paid parking during study-associated appointments through the study.

## **6** STUDY INTERVENTION

#### 6.1 STUDY INTERVENTION(S) ADMINISTRATION

#### 6.1.1 STUDY INTERVENTION DESCRIPTION

The study intervention is participation in a supervised exercise program. Participants will perform two exercise sessions per week, with at least one day between sessions. All participants will perform a standardized set of general resistance exercises targeting the chest, shoulders, back, upper and lower extremities, and core. In addition, those participants allocated to the high intensity neck strengthening group will also perform manual resistance exercises in sagittal plane flexion and extension, coronal plane lateral flexion in both directions, and axial plane rotation in both directions, as well as dumbbell shoulder shrugs.

## 6.1.2 INTERVENTION ADMINISTRATION

The supervised exercise program will be administered by a Certified Strength and Conditioning Specialist. Manual resistance exercises will be performed lying horizontally on a standard weight lifting bench using a similar protocol as previously described by our group. For each repetition, the CSCS will apply steady manual resistance through the both the concentric and eccentric phases of cervical range of motion. Shoulder shrugs will be performed at a tempo allowing for steady controlled movement to be maintained throughout the concentric and eccentric phases with a brief pause at the top of the shrug motion using the maximum load comfortably completed by each participant for the target number of repetitions while maintaining correct form. The high intensity neck strengthening exercise program will increase in volume and intensity over the study duration to accommodate muscular fitness adaptation. All exercises were performed in accordance with National Strength and Conditioning Association standards.

#### 6.2 MEASURES TO MINIMIZE BIAS: RANDOMIZATION AND BLINDING

Subjects will be randomized using a centralized electronic randomization tool with equal allocation to the control and high-intensity neck strengthening groups. Balanced block randomization will be used to ensure equal sex and age category balance between the groups. Age category will correspond to high school under-class (i.e., age 13.0 - 16.49 years at the time of randomization) vs. upper-class (i.e., age 16.50 – 19.99 years) status given the typical maturation occurring in adolescents through the high school years. Subjects will be considered enrolled in the trial upon randomization and available data will be included in the intention to treat analysis. The Study Statistician, Strength Coach, Study Coordinator, and PI (or his Co-I designee when necessary to make a determination of AE relatedness to the study) will not be blinded to subject group allocation. Other members of the study team, including those responsible for performing the laboratory- and radiology-based assessment will be blinded to group allocation status. Subjects will not be informed of their group allocation status, although they will be aware of whether or not they are performing neck strengthening exercises during their exercise sessions. Subjects will be instructed not to discuss whether they are performing neck strengthening exercises during their exercise sessions.

## 6.3 STUDY INTERVENTION COMPLIANCE

Subjects will be given the opportunity to make-up any missed exercise sessions within 7 days of the originally scheduled date, so long as at least one day of rest is scheduled between successive exercise sessions. Subjects will be considered to have successfully completed the exercise protocol if at least 20 of the 24 exercise sessions are attended, with no more than 2 missed sessions during any 4-week block.

## 6.4 CONCOMITANT THERAPY

Participation in a resistance training exercise program including exercises specifically intended to target the neck muscles either in the 3 months prior to study enrollment or a plan to begin participating in such an exercise program outside of the study protocol at any point during the 12-week study period are criteria for exclusion.

## 6.4.1 RESCUE MEDICINE

N/A

# 7 STUDY INTERVENTION DISCONTINUATION AND PARTICIPANT DISCONTINUATION/WITHDRAWAL

## 7.1 DISCONTINUATION OF STUDY INTERVENTION

Discontinuation from the exercise intervention does not necessarily mandate immediate discontinuation from the study. If a subject is unable to continue participating in their assigned exercise intervention due to injury, illness, or other reason, they will still be eligible to complete all or part of the next scheduled study assessment(s) so long as they are able to do so within 7 days of discontinuation of the intervention, they have completed at least 4 exercise sessions since their last assessment was performed, and they remain able to participate in the upcoming lab-based (and MRI, as applicable) assessment. If a clinically significant finding is identified (including, but not limited to changes from baseline) after enrollment, the PI or qualified designee will determine if any change in participant management is needed. Any new clinically relevant finding will be reported as an adverse event (AE).

The data to be collected at the time of study intervention discontinuation will include the following:

- Date and reason for study intervention discontinuation
- Eligibility for and ability to perform upcoming study assessments

## 7.2 PARTICIPANT DISCONTINUATION/WITHDRAWAL FROM THE STUDY

Participants are free to withdraw from participation in the study at any time upon request.

An investigator may discontinue or withdraw a participant from the study for the following reasons:

- Pregnancy, unless written clearance to continue study participation is provided by the treating obstetrician or other physician managing the pregnancy
- Significant study intervention non-compliance

- If any clinical adverse event (AE) or other medical condition or situation occurs that precludes the subject's ability to participate in the study or such that continued participation in the study would not be in the best interest of the participant
- If the participant meets an exclusion criterion (either newly developed or not previously recognized) that precludes further study participation
- Participant unable to participate in study exercise program for 14 or more consecutive days.

The reason for participant discontinuation or withdrawal from the study will be recorded on the Case Report Form (CRF). Subjects who are randomized and drop out subsequently will not be replaced.

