# 7.3 LOST TO FOLLOW-UP

A participant will be considered lost to follow-up if he or she fails to return for 4 scheduled visits or more than 14 days and is unable to be contacted by the study team.

The following actions must be taken if a participant fails to return for a required study visit:

- The study team will attempt to contact the participant and reschedule the missed visit as soon as possible and counsel the participant on the importance of maintaining the assigned visit schedule and ascertain if the participant wishes to and/or should continue in the study.
- Before a participant is deemed lost to follow-up, the investigator or designee will make every effort to regain contact with the participant (where possible, multiple telephone calls, emails, and/or text messages, and, a certified letter or equivalent may be sent to the participant's last known mailing address or local equivalent methods). These contact attempts will be documented in the participant's study file.
- Should the participant continue to be unreachable, he or she will be considered to have withdrawn from the study with a primary reason of lost to follow-up.

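### Section 7.2 lets an athlete who paused for two weeks and came back be withdrawn from the whole study, even where 6.3 counts the programme as completed, so the Time Point 4 value can be lost

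*Combined protocol and SAP*

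**What the plan says.** - **Withdrawal (7.2).** The list opens with "An investigator may discontinue or withdraw a participant from the study for the following reasons" and includes "Participant unable to participate in study exercise program for 14 or more consecutive days". The withdrawal is from the study, not only from exercise. No exception is made for an athlete who resumes training or who still satisfies 6.3. The list also names significant non-compliance, without tying it to the 6.3 limits. The section ends: "Subjects who are randomized and drop out subsequently will not be replaced".
- **Compliance (6.3).** The exercise protocol counts as successfully completed if "at least 20 of the 24 exercise sessions are attended, with no more than 2 missed sessions during any 4-week block". Subjects may "make-up any missed exercise sessions within 7 days of the originally scheduled date", with a rest day kept between sessions.
- **Frequency (6.1.1).** "Participants will perform two exercise sessions per week, with at least one day between sessions".
- **Stopping exercise (7.1).** Stopping the exercise need not end study participation. Further assessment is then conditional: within 7 days of stopping, after at least 4 sessions since the last assessment, and if the athlete is able to take part.
- **Blinding and analysis set (6.2, 9.3).** The PI is unblinded. After randomization, "available data will be included in the intention to treat analysis", and 9.3 keeps participants with partial data.
- **Primary endpoint (synopsis, section 3).** It is measured at Assessment Time Point 4. Section 9.4.2 analyses it with a linear mixed model over the four time points.

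**The concern.** The point is about athletes who pause, for instance through illness or injury, and then return. One section can call such an athlete a successful completer while another makes the same gap a reason to end all further study visits. Nothing ranks the two sections, and nothing provides for Time Point 4 after a 7.2 withdrawal.

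Two things are at stake. One is precision: Time Point 4 is the endpoint visit and carries most of an athlete's information about the slope. The other is the integrity of the randomised comparison. Whether a returned athlete supplies the endpoint can depend on a discretionary decision by someone who knows the arm, and two decision-makers could treat the same absence in opposite ways. Including available data, as 6.2 and 9.3 promise, does not create a measurement that was never taken.

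**Working it through.** **1. The plan's own power figure.** Section 9.2 gives 30 per arm, d = 0.6 to 1.0, a slope variance factor of 9/14 and power of .83 at d = 0.6. Section 9.4.1 gives alpha .05; two-sided is assumed here.

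Slope effect = 0.6 × √(14/9) = 0.748.

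Power = Φ(0.748 × √(30/2) − 1.96) = Φ(2.898 − 1.960) = Φ(0.938) = .826. With the plan's rounded factor of 1.25 it is .828. The stated .83 is reproduced.

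**2. Sessions in a 14-day gap.** At two fixed days a week: 2 × 2 = 4. There are 24 sessions in three blocks of 8. Section 6.3 tolerates 24 − 20 = 4 missed, with at most 2 in a block.

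**3. Does such a gap pass 6.3?**

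| Gap | Missed by block | Attended | 6.3 met? |
|---|---|---|---|
| Weeks 4-5, no make-ups | 2, 2, 0 | 20 of 24 | Yes |
| Weeks 8-9, no make-ups | 0, 2, 2 | 20 of 24 | Yes |
| Weeks 2-3, no make-ups | 4, 0, 0 | 20 of 24 | No (4 > 2 in a block) |

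Make-ups rescue some other positions. Take an absence on days 1-14, with later regular sessions left on their days:

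- Sessions on days 5 and 7 of each week: days 5, 7, 12 and 14 are missed. The last two can be made up on days 15 and 17, before the regular sessions on days 19 and 21. Two remain missed, so 6.3 is met.
- Sessions on days 1 and 3 of each week: days 1, 3, 8 and 10 are missed. The make-up windows close on days 15 and 17, both regular session days, and day 16 leaves no rest day. Four remain missed, so 6.3 is not met.

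**4. All placements.** Of the 21 pairs of weekdays, 14 keep a rest day. An 84-day programme has 84 − 14 + 1 = 71 start days for the gap, so there are 14 × 71 = 994 cases.

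- No make-ups: 108 of 994 (11%) meet 6.3. These are the gaps that split two and two across a block boundary.
- Make-ups allowed (after day 84 too), regular sessions fixed: 346 of 994 (35%). At most two sessions can be made up.

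These are shares of possible placements, not expected frequencies in the trial.

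**5. Cost of losing Time Point 4.** The 9/14 factor matches a slope from a fixed baseline with later visits at times 1, 2 and 3, expressed as change at time 3: 3²/(1 + 4 + 9) = 9/14. This is an inference; the plan does not derive it. Without Time Point 4 it becomes 9/(1 + 4) = 9/5, which leaves (5/9)/(14/9) = 5/14 = 36% of the information.

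If a fraction w of each arm loses only Time Point 4, the effective n is 30 × [(1 − w) + w × 5/14]:

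| w (assumed) | Effective n per arm | Power at d = 0.6 |
|---|---|---|
| 0 | 30.0 | .826 |
| 5% | 29.0 | .814 |
| 10% | 28.1 | .801 |
| 20% | 26.1 | .772 |

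**The case against.** The strongest reply is that the sections do different jobs. Section 6.3 labels adherence afterwards by counting sessions. Section 7.2 is permissive, speaks of inability rather than any absence, and compels nobody to withdraw an athlete who has returned. Section 7.1 already separates stopping exercise from leaving the study. The mixed model keeps earlier visits. The enrolment margin can also absorb lost precision: with 36 per arm and no other losses, 20% losing Time Point 4 gives an effective n of 36 × (0.8 + 0.2 × 5/14) = 31.4 and power of .842.

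Most of this stands, and it limits the point to a possible loss. It does not remove it. An athlete who was unable to train and then recovered is exactly the case 7.2 describes. Section 7.1 addresses athletes who cannot continue and leaves the 7.2 ground in force. The mixed model can allow for withdrawal explained by arm and earlier measurements, but not for withdrawal linked to the Time Point 4 result the athlete would have had. Enrolling more athletes does not correct that.

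Four stronger readings are tempting and are not supported:

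- **Any two-week gap passes 6.3 once make-ups are used.** That needs later regular sessions to move and make-ups after week 12, and 6.3 settles neither. With regular sessions fixed and the programme ending at week 12, only 2 of the 11 whole-week gaps pass on 12 of the 14 schedules.
- **The effect would be materially overstated.** That requires giving no benefit to athletes who attended at least 20 of 24 sessions. Suppose instead that benefit tracks attendance and 10% of the neck arm (assumed) were withdrawn and wholly missing. The all-randomised log effect is log(.8) × (0.9 + 0.1 × 20/24) = −0.219, a 19.7% reduction against 20%, or about 1.7% on the log scale. Retained earlier visits would change even that.
- **Section 7.3 does the same.** It covers an athlete who "fails to return for 4 scheduled visits or more than 14 days and is unable to be contacted by the study team", and requires documented contact efforts first. It does not reach returned athletes.
- **The decision-maker always knows the arm.** Section 7.2 says an investigator. Section 6.2 names the PI as unblinded, and a Co-I only when standing in to judge adverse event relatedness.

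**Conclusion.** The inconsistency is real but limited. The same 14-day gap can be successful completion under 6.3 and a ground for full withdrawal under 7.2, always when it splits two and two across a block boundary and in some further positions with make-ups. Time Point 4 can then be lost for a returned athlete, permanently and without replacement.

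The power cost is small to moderate: from about .83 to about .81, .80 or .77 for assumed losses of 5%, 10% or 20%. This rests on a two-sided test, equal loss in both arms, retained earlier visits and the inferred origin of 9/14. The documents give no withdrawal rate. The bias from a decision by someone who knows the arm is a risk whose size and direction cannot be computed from the documents, and the 20% drop-out allowance does not address it. This is worth correcting, but it does not undermine the design.

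**What to change.** Reconcile 6.3, 7.1 and 7.2 so that a given absence has one stated consequence. Which exercise threshold applies is for the sponsor, and the safety, pregnancy and exclusion grounds in 7.2 are outside this point. Say in 6.3 whether regular sessions may move to accommodate make-ups.

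Add to 7.2 that exercise absence or non-compliance alone does not end the scheduled laboratory assessments, including Time Point 4, of an athlete who has returned and is able and willing to be tested.

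The cost is a few lines of wording and visits already in each athlete's schedule. The downside is that some athletes are tested after less exercise, which an intention-to-treat analysis accepts. Handing the decision to a blinded team member is not a good substitute. That group includes the laboratory and radiology assessors, and reviewing reasons for exercise absence could reveal the arm to them.

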# 7.3 LOST TO FOLLOW-UP

A participant will be considered lost to follow-up if he or she fails to return for 4 scheduled visits or more than 14 days and is unable to be contacted by the study team.

The following actions must be taken if a participant fails to return for a required study visit:

- The study team will attempt to contact the participant and reschedule the missed visit as soon as possible and counsel the participant on the importance of maintaining the assigned visit schedule and ascertain if the participant wishes to and/or should continue in the study.
- Before a participant is deemed lost to follow-up, the investigator or designee will make every effort to regain contact with the participant (where possible, multiple telephone calls, emails, and/or text messages, and, a certified letter or equivalent may be sent to the participant's last known mailing address or local equivalent methods). These contact attempts will be documented in the participant's study file.
- Should the participant continue to be unreachable, he or she will be considered to have withdrawn from the study with a primary reason of lost to follow-up.

# 8 STUDY ASSESSMENTS AND PROCEDURES

# 8.1 EFFICACY ASSESSMENTS

**Methodology for measuring kinematic outcome:** Net head acceleration will be measured under direct force application, as well as standardized checking/blocking and voluntary soccer heading tasks at 4 time points (see Section 1.3). Our rationale for including loading conditions involving direct force application to the head as well as force application to the body with resultant transmission of inertial forces to the head (the simulated checking/ blocking task) is that concussions can, by definition, occur as a result of both of these mechanisms. Voluntary soccer heading is being used as a second, more ecologically-valid direct loading condition. The order of testing will be randomized across subjects and practice trials will be performed for each task prior to data collection to familiarize subjects with each procedure.

## Loading conditions:

Standardized direct force application to the head in forced flexion, extension, lateral flexion, and axial rotation. We will use a customized laboratory testing apparatus to deliver controlled forces to the head via headgear connected to cable with in-line weight-drop, similar to as previously described by our group. The results of three trials will be averaged, in each direction during active isometric neck muscle pre-contraction (as if bracing in anticipation of being struck in the head during live play) as well as during relaxed upright sitting (to simulate an unanticipated blind-side impact)

conditions. An effort will be made to prevent subjects' knowledge of the precise timing of force application during the unanticipated condition using strategies such as wearing blinders and being exposed to ambient white noise. sEMG will be used as biofeedback to ensure appropriate neck muscle activation under both conditions, in a similar manner as in our previous pilot study.

Standardized impacts to the body will be applied in the coronal plane by swinging a boxer's heavy punching bag suspended from the ceiling like a pendulum into the subject's lateral shoulder to simulate a sport checking or blocking event. Subjects will stand on a force plate in an athletic ready position so that the punching bag surface lightly touches the lateral aspect of their shoulder while hanging at rest. The punching bag will be drawn back in a standardized manner and released to elicit lateral flexion of the head and neck in the coronal plane upon impact to the shoulder (monitoring to ensure they are not displaced from the force plate). The results of three trials will be averaged during active pre-contraction of the neck and torso muscles (as if bracing in anticipation of being checked or blocked by an opponent during live play) as well as a relaxed upright standing (to simulate an unanticipated blind-side collision) conditions. An effort will again be made to prevent subjects' knowledge of the precise timing of force application during the unanticipated condition using strategies such as wearing blinders and being exposed to ambient white noise. sEMG will again be used to ensure appropriate neck muscle activation under both conditions, as above.

Standardized voluntary soccer headers will also be performed in the sagittal plane. One heading task will involve an active heading strategy with the goal of returning a soccer ball directly back in the direction from which it was pitched with as much velocity as possible, as if performing an attacking/offensive soccer header. A second heading task will be similar, except with a goal of gently directing the soccer ball to the ground in the direction from which it was pitched as if performing a glancing header to pass the ball to the foot of a teammate. For both tasks, a standard soccer ball inflated at the low end of the recommended inflation range) will be pitched to the subject from a soccer machine using similar methodology as has been applied in previous soccer heading studies. The results of three trials will be averaged under both heading strategies.

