Objectives:		Primary Objective (AIM 1): To determine the effect of manual resistance neck strengthening exercise on net head acceleration during simulated sport-associated impacts to the head (direct loading condition). Secondary Objective (AIM 1): To determine the effect of manual resistance neck strengthening exercise on net head acceleration during simulated sport-associated impacts to the body (indirect loading condition). Exploratory Objective (AIM 1): To determine the effect of manual resistance neck strengthening exercise over time on neck strength, cervical muscle volume, neuromuscular recruitment, and net head acceleration under direct and indirect loading as well as during voluntary soccer heading. Exploratory Objective (AIM 2): To determine the relative influences of baseline neck strength and cervical muscle volume on net head acceleration during simulated sport-associated impacts to the head and body with and without volitional, anticipatory cervical muscle pre- contraction to brace for the impact.

Endpoints:	Primary Endpoint: Mean area under the net head acceleration vs. time curve during direct loading, with anticipatory bracing, at Assessment Time Point 4.
	Secondary Endpoint: Mean area under the net head acceleration vs. time curve during indirect loading, with anticipatory bracing, at Assessment Time Point 4.
Study Population:	Up to 72 male and female high school soccer athletes in and around Ann Arbor Michigan.
Phase:	N/A
Description of	University of Michigan.
Sites/Facilities Enrolling	
Participants:	
Description of Study	Neck strengthening resistance exercise.
Intervention:	
Study Duration:	Approximately 60 months.
Participant Duration:	Approximately 4 months.

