Scientific Premise for AIM 2: AIM 2 is based on the scientific premise that anticipatory precontraction of the cervical muscles to brace for an impact influences head acceleration. Furthermore, cervical muscle attributes (i.e., neck strength and cervical muscle volume) influence head acceleration differently with vs. without cervical muscle pre-contraction. This premise is supported by our own work demonstrating that head acceleration, again reported as  $\Delta V$  and  $\Delta \omega$ , decreased by 12.3% and 9.7%. respectively, during anticipatory cervical muscle pre-contraction as compared to relaxed, upright sitting. Recent finite element modeling work, as well as numerous other studies in the concussion and whiplash literature, have also reported decreased head acceleration in response to various forms of loading during trials with vs. without anticipation and/or cervical muscle pre-contraction. However, the design of those studies limits the insight they can provide into which cervical muscle attribute is most responsible for controlling head acceleration with vs. without anticipatory pre-contraction. While not the primary objective, our previous work demonstrated greater neck strength and circumference were each significantly associated with lower  $\Delta V$  and  $\Delta \omega$  across all directions of head motion under both anticipation conditions (r= .42 to r= .60 for neck strength; r= .60 to r= .76 for neck circumference). In that study, more of the variability in head acceleration was explained by neck strength for 6 of the 7 models under the anticipated condition, but by neck circumference for 6 of the 7 models without anticipation. That finding suggests neck strength and cervical muscle volume may influence head acceleration differently depending on cervical muscle pre-contraction status. We are unaware of other reports to directly quantify the relationships between individual cervical muscle attributes and head acceleration with vs. without anticipatory cervical muscle pre-contraction.

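### In the checking/blocking task, torso bracing (and possibly stance) changes together with neck bracing, so in AIM 2 a braced-versus-unbraced difference for body impacts cannot be credited to cervical pre-contraction alone

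*Combined protocol and SAP*

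**What the plan says.** Section 8.1 (Loading conditions, standardized impacts to the body) sets the starting posture once, with no restriction to one condition: "Subjects will stand on a force plate in an athletic ready position so that the punching bag surface lightly touches the lateral aspect" of the shoulder. The braced trials are then run "during active pre-contraction of the neck and torso muscles" and the unbraced trials "as well as a relaxed upright standing (to simulate an unanticipated blind-side collision) conditions". In the unbraced trials an effort is made to hide the moment of impact, "using strategies such as wearing blinders and being exposed to ambient white noise". The stated check on the manipulation is that "sEMG will again be used to ensure appropriate neck muscle activation under both conditions".

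The Synopsis (1.1) states the AIM 2 objective in terms of "impacts to the head and body with and without volitional, anticipatory cervical muscle" pre-contraction. Section 3 and the AIM 2 premise in 2.2 use the same cervical label. Section 9.4.8 fits linear models for direct and indirect loading under each anticipation condition. It computes the change in R² when neck strength or muscle volume is removed, bootstraps confidence intervals, and draws a conclusion for the given condition.

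**The concern.** The AIM 2 premise concerns the neck: active muscle stiffness should track strength when the neck muscles are contracted, and passive stiffness should track muscle volume when they are not. Testing it calls for two conditions that differ in neck contraction and in as little else as possible. In the checking task the impact enters at the shoulder and reaches the head through the trunk. How firmly the trunk is held, and how the athlete stands, could therefore plausibly affect head motion by a route other than the neck muscles.

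Suppose strength turned out to matter more in the braced body impacts and volume more in the unbraced ones. The premise would predict that pattern, but trunk bracing, or a change of posture, would be a competing explanation. What is at stake is the mechanistic reading of AIM 2 for body impacts.

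**Working it through.** No arithmetic applies: the point concerns how the conditions are defined, and the plan gives no figure to reproduce. The definitions in 8.1 can be set side by side.

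| Feature | Direct, braced | Direct, unbraced | Checking, braced | Checking, unbraced |
|---|---|---|---|---|
| Neck muscles | pre-contracted | relaxed | pre-contracted | relaxed |
| Torso muscles | not mentioned | not mentioned | pre-contracted | relaxed (implied) |
| Posture | not stated for this condition | upright sitting | ready position | ready position (general sentence) or upright standing (condition sentence) |
| Load timing | no concealment described | concealed | no concealment described | concealed |
| Check described | neck sEMG | neck sEMG | neck sEMG | neck sEMG |

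1. **Torso.** This difference is explicit. Torso pre-contraction belongs to the braced checking condition by definition and has no counterpart in direct loading.

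2. **Stance.** This difference is not established. The general sentence, "Subjects will stand on a force plate in an athletic ready position", covers all trials; the description of the unbraced trials says upright standing. Either the stance differs between conditions or the two sentences conflict. If it differs, bag contact height and whole-body stiffness may differ as well, but that follows only on this reading.

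3. **Can the planned data separate these factors?** The sEMG sites in 8.1 are the sternocleidomastoid, upper trapezius, splenius capitis and semispinalis capitis, all treated as cervical muscles. No other trunk or leg site is listed. The force plate is mentioned as the standing surface and for checking that subjects are not displaced from it. Markers track the head relative to the torso, but no criterion for matching posture is given. Randomizing test order does not separate factors bundled within one condition. The models in 9.4.8 use strength and volume as predictors and contain no term for trunk activation or posture.

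4. **Which inference is affected?** The rule in 9.4.8 compares strength with volume inside one condition, and that ranking can be computed and read as it stands. The comparison across conditions, which the premise in 2.2 needs, is the one that loses its cervical interpretation.

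5. **What kind of disturbance would matter?** If trunk bracing or stance multiplied every athlete's head acceleration by the same constant c, then log(c·y) = log(c) + log(y). Only the intercept moves, and R² is unchanged. On the raw scale the residual and total sums of squares are both multiplied by c², so R² = 1 − SS(residual)/SS(total) is again unchanged. A uniform shift therefore leaves every differential R² where it was. An effect that varies between athletes can alter it, for example if athletes with stronger necks also brace the trunk more effectively. The documents neither exclude nor quantify such variation.

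**The case against.** Torso bracing looks deliberate. The task is meant to imitate being checked or blocked in play, where an athlete braces the whole upper body, and the protocol values realism under laboratory control. Parts of 2.2 and Section 3 also speak of anticipated versus unanticipated impacts, a label these conditions fit. Upright standing may describe muscle state rather than posture, in parallel with upright sitting in direct loading. A Manual of Procedures is mentioned in 10.1.9 and may fix the stance. AIM 2 is exploratory.

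Most of this stands, and it narrows the point. It does not remove it: the stated objective names cervical pre-contraction for body impacts too, and a sound reason for bracing the torso does not make the contrast specific to the neck.

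A reader might infer three stronger things that the documents do not support.

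- **That the trials certainly differ in stance.** The text is ambiguous.
- **That AIM 2 as a whole fails, with direct loading as a clean comparator.** Direct loading has no described torso component, so it isolates the neck better. It is not perfectly clean, because timing concealment differs between its conditions, and that its braced trials are also seated is inferred.
- **That the distortion can be expressed as a percentage by setting an assumed stance effect against the group's earlier bracing effects of 12.3% and 9.7%.** Those were obtained "during anticipatory cervical muscle pre-contraction as compared to relaxed, upright sitting", which is not the checking task. The documents give no stance or trunk effect, and 9.4.8 specifies no test of the mean braced-minus-unbraced difference.

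**Conclusion.** The point holds for the indirect-loading part of exploratory AIM 2. There, a between-condition difference in the relative influence of strength and volume reflects neck and torso bracing together with anticipation, and possibly stance. It cannot be assigned to cervical pre-contraction alone. The torso element rests on explicit wording; the stance element rests on two sentences that need reconciling. No numerical size can be given from the documents, and bias in differential R² requires trunk or stance effects that vary between athletes.

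The within-condition rankings and the direct-loading part of AIM 2 are not invalidated. Nor are the primary and secondary endpoints, which use braced trials and compare randomized groups. This is an inexpensive correction to what an exploratory aim may claim.

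**What to change.** 1. In 8.1, reconcile the two stance statements, and use one stance and one bag alignment for both indirect conditions.
2. Matching stance leaves torso bracing bundled with neck bracing. So, for all athletes, describe the indirect contrast in the AIM 2 objective (1.1 and Section 3) and in 9.4.8 as whole-body bracing/anticipation. Add stance to that description for any athletes tested in two stances.
3. Base any statement specific to cervical pre-contraction on direct loading, and note there that concealment of load timing differs between conditions.

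The cost is a few sentences in the protocol and the laboratory manual, with no new data. The exploratory claim for body impacts becomes narrower, and the unbraced trials may lose a little blind-side realism. If stance changes mid-trial, unbraced trials before and after the change should be flagged in the data set. The secondary endpoint's measurement is unaffected provided the common stance is the one in which the braced trials are already run; choosing otherwise would alter those trials too.
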